## BACKGROUND

Securing the airway is a fundamental priority in the treatment of critically ill or injured patients. In the regular OR setting, direct laryngoscopy is the primary method for performing endotracheal intubation. But even in experienced hands, along with regular training and practice, successful endotracheal intubation sometimes requires additional tools to assist endotracheal intubation. Airway complications are rare but may lead to severe complications, such as brain damage and even death. Set aside the “cannot ventilate and cannot intubate” scenario, difficult intubation has been associated with significant patient morbidity. For example, repeated intubation attempts are associated with respiratory and hemodynamic complications, including hypoxemia, cardiac arrest, regurgitation, aspiration, and airway trauma — along with bradycardia and cardiac arrest in emergency settings.

Rapid Sequence Intubation (RSI) is indicated when patients are not fully conscious or are otherwise at increased risk of gastric regurgitation and aspiration. The main objective of this technique is to minimize the time interval between loss of protective airway reflexes and tracheal intubation with a cuffed endotracheal tube. The period between induction of general anesthesia and securing the airway is most critical since aspiration of gastric content is then most likely. However, rapid sequence induction is associated with, hemodynamic instability and oxygen desaturation. It's therefore crucial to minimize the number of intubations attempts and the time to intubation, as both prolonged time to intubation and multiple intubation attempts significantly attribute to perioperative morbidity and mortality.

Videolaryngoscopes were introduced into clinical practice approximately two decades ago and have gained wide acceptance in the elective OR setting. Videolaryngoscopes can facilitate endotracheal intubation by improving visualization of the larynx, thereby facilitating direct observation of the tracheal tube during passage through the vocal cords. Consequently, videolaryngoscopy may decrease intubation difficulties and ultimately increase first-attempt and overall intubation success rate. However,

available literature is heterogeneous in study design, patient characteristics, and intubation provider experience.

Several trials demonstrated that videolaryngoscopes improve vocal cord visualization, but not first-pass intubation success. Interestingly, in a trial with ICU patients, videolaryngoscopy did not improve first-attempt intubation success and was associated with severe complications including death, cardiac arrest, cardiovascular collapse and hypoxemia. In contrast, other trials reported improved glottis visualization, improved first-pass success and no difference in rate of complications compared with direct laryngoscopy. In a recent Cochrane review of more than seven thousand patients with and without difficult airways, videolaryngoscopy was associated with fewer complications (e.g., laryngeal or airway trauma, postoperative hoarseness, hypoxia), fewer failed intubations, and no increase in the time required for intubation. The extent to which videolaryngoscopes might facilitate intubation in patients undergo RSI is unclear.

The McGrath (Medtronic, Minneapolis, MN) is an FDA-approved and commercially available videolaryngoscope that includes a Macintosh blade and a camera which provides an indirect view of the glottis. The McGrath has been tested in a variety of settings and consistently provides better glottis visualization than direct laryngoscopy in patients with difficult airways. However, its suitability in the context of RSI has yet to be formally evaluated, and whether results from previous trials apply to these patients remains unknown.

## Objectives and Hypothesis

Our goal is to compare conventional direct laryngoscopy using a Macintosh blade with the McGrath videolaryngoscope for rapid sequence endotracheal intubation. Specifically, we propose to test the primary hypothesis that videolaryngoscopy improves visualization of the vocal cords, defined using the modified Cormack and Lehane classification (primary outcome), versus direct laryngoscopy.

We will also test the secondary hypotheses that McGrath videolaryngoscopy decreases number of intubation attempts and the number of intubation failures. We hypothesize that the McGrath videolaryngoscopy reduces both, the number of intubation attempts and the number of intubation failures.

We will also assess the following exploratory outcomes:

1. Ease of intubation;
2. Glottis opening score (POGO) score;
3. Duration of intubation.

We will also assess the following safety outcomes:

1. Incidence of cut lips, airway injury, or dental injury;
2. Incidence of postoperative coughing;
3. Incidence or severity of postoperative sore throat;
4. Incidence or severity of postoperative hoarseness.

## METHODS

### Design

We propose a patient-blind multi-center randomized trial that will be coordinated by the Department of Outcomes Research at the Cleveland Clinic, Main Campus.

### Patients

We will enroll up to 800 (including 25 – 50 pilot) consenting adults, with American Society of Anesthesiologists (ASA) physical status 1-3, who are scheduled for elective non-cardiac surgery requiring endotracheal intubation with rapid sequence induction for general anesthesia. Written informed consent will be obtained. Participating study centers will be:

- Cleveland Clinic, Main Campus, Cleveland OH
- Tabriz University of Medical Sciences, Tabriz, Iran
- The University of Health Science, Konya City Hospital, Konya, Turkey
- The University of Health Science, Bakırköy [name] Education, and Research Hospital, Istanbul, Turkey

#### Inclusion criteria

1. Age between 18 and 99 years;
2. American Society of Anesthesiologists (ASA) physical status 1-3;
3. Elective surgery requiring oral endotracheal intubation for general anesthesia;
4. Any clinical indication for rapid sequence induction as determined by the attending anesthesiologist;
5. Anticipated extubation in the operating room.

#### Exclusion criteria

1. Refusal of participation by attending anesthesiologist;
2. Indicated fiberoptic awake intubation

3. Body Mass index (BMI) > 45 kg/m^2.

## Protocol

In the preoperative period, airway details for participating patients will be recorded by a research coordinator or anesthesia provider. Patients will be positioned supine and in a standardized ramped position on the OR table. Patients will be pre-medicated with midazolam, as clinically appropriate. All patients will be pre-oxygenated until the fraction of expired oxygen exceeds 80%.

Rapid sequence induction will be induced as preferred by the attending anesthesiologist, usually with a combination of lidocaine 1 mg/kg, propofol 2-5 mg/kg, fentanyl 1-3 µg/kg, and succinylcholine 1.5 mg/kg or rocuronium 1.0 mg/kg. Complete muscle relaxation will be confirmed by absence of palpable twitches in response to supra-maximal train-of-four stimulation of the ulnar nerve at the wrist.

Patients will be randomized 1:1 before induction, stratified for primary anesthesia providers (*experienced* – specialist, attending vs. *unexperienced* – trainees) to:

- Direct laryngoscopy using an appropriately sized Macintosh blade (usually size 3 or 4);
- McGrath videolaryngoscope in an appropriate size (usually blade size 3 or 4).

Randomization will be based on computer-generated codes accessed from the Redcap system.

Intubations will be performed with a regular endotracheal tube of adequate diameter, usually 7.0 mm to 8.0 mm. Endotracheal tubes will be equipped with a hockey-stick-shaped stylette, which will be prepared by the anesthesiologist in advance. The McGrath or the Macintosh blade will be introduced into oral cavity according to manufacturer recommendations and clinical practice. Minor airway manipulation procedures including BURP or Sellick maneuvers will be allowed to improve

visualization of the vocal cords. If initial intubation attempts fail, the endotracheal tube will be removed. Minor adjustments of patient's position and/or tube stylette will be used as clinically appropriate. Up to two intubation attempts will be made as necessary. Further airway management will follow clinical assessment of the anesthesiologist. The anesthesiologist will be permitted to terminate study participation and switch to an alternative method.

Once intubation is achieved, the endotracheal tube will be connected to the anesthesia circuit, and the endotracheal cuff pressure will be measured placed between 25 and 30 cm H2O.

Mechanical ventilation with O2 and air will be adjusted to maintain end-tidal PCO2 between 32 and 35 mmHg as clinically necessary. Maintenance of general anesthesia will be provided, as clinically indicated.

At the end of the surgical procedure, patients will be extubated and transferred to the post anesthesia care unit (PACU). Patients will then be assessed for postoperative complications 2 hours following extubation, or at PACU discharge.

## **Measurements**

Demographic and morphometric characteristics will be collected from electronic medical records.

1. Age
2. Sex
3. Race
4. BMI
5. ASA status
6. Airway examination
  - a. History of obstructive sleep apnea (yes/no)
  - b. History of snoring (yes/no)

- c. History of CPAP (yes/no)
- d. History of difficult airway (yes/no)
- e. Mobility of cervical spine (0, 15, 30, and 45 degrees)
- f. Mouth opening (cm)
- g. Inter-incisor gap (cm)
- h. Mandibular protrusion test (Class A, B, C)
- i. Thyro-mental distance (cm)
- j. Thyro-mental height (cm)
- k. Sterno-mental distance (cm)
- l. Neck circumference (cm)
- m. Upper lip bite test (Class I, II, III)
- n. Mallampati score (1/2/3/4)
- o. Teeth status (Edentulous, missing frontal teeth or full dentition)

## Outcomes

### Primary outcome:

Best glottis visualization, defined as visualization according to the modified Cormack and Lehane classification

Original Cormack and Lehane system	1 Full view of the glottis	2 Partial view of the glottis or arytenoids	3 Only epiglottis visible	4 Neither glottis nor epiglottis visible
View at laryngoscopy				
Modified system	1 As for original Cormack and Lehane above	2a Partial view of the glottis	2b Arytenoids or posterior part of the vocal cords only just visible	3 As for original Cormack and Lehane above

**Secondary Outcomes:**

- Intubation attempts, defined as introducing the endotracheal tube into oral cavity to perform endotracheal intubation (1, 2, 3, etc.)
- Intubation failure, defined as
  - Failure to intubate within 3 intubation attempts
  - Need to switch intubators or intubation device
  - Need to stop study per anesthesiologist's discretion

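### The procedure gives a limit of two intubation attempts, the failure outcome a limit of three, and nothing reconciles them (minor)

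*Combined protocol and SAP*

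**What the plan says.** The Protocol section describes the procedure in order. On failure, "If initial intubation attempts fail, the endotracheal tube will be removed", and position or stylette may be adjusted. Then: "Up to two intubation attempts will be made as necessary". After that, "Further airway management will follow clinical assessment of the anesthesiologist", and "The anesthesiologist will be permitted to terminate study participation and switch to an alternative method".

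Under Secondary Outcomes, intubation failure has three criteria:

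1. "Failure to intubate within 3 intubation attempts"
2. "Need to switch intubators or intubation device"
3. "Need to stop study per anesthesiologist's discretion"

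The other secondary outcome, number of attempts, is counted on an open scale that runs to three and beyond: "introducing the endotracheal tube into oral cavity to perform endotracheal intubation (1, 2, 3, etc".

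The statistical section on secondary outcomes tests failure by chi-square and reports a relative risk with a 97.5% confidence interval. Each of the two secondary hypotheses is judged at 0.025. The Design section describes blinding of the patient only.

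**The concern.** The procedure and the endpoint give different attempt limits. If the procedure means two attempts in total, the endpoint threshold lies one attempt beyond it. Two patients with the same history, two failed attempts by one operator with the assigned device, can then be scored differently according to what the operator does next. A successful third try is not a failure; a change of operator or device, or a study stop, is.

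That decision is made by someone who knows which laryngoscope is in use, and the outcome is formally tested. Four centres take part, and without a common rule they may read the two numbers differently. If operators were readier to persist with one device than with the other, the relative risk would partly reflect that habit.

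**Working it through.** **No plan figure to reproduce.** The plan gives no event rate, power or sample size for intubation failure. The 384 patients in the sample size paragraph are for the primary outcome and do not enter here.

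**Scoring after two failed attempts with the assigned device**

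| What happens next | Criterion 1 | Criterion 2 | Criterion 3 | Score |
|---|---|---|---|---|
| Third attempt, same operator and device, succeeds | not met | not met | not met unless a stop is declared | not a failure |
| Third attempt, same operator and device, fails | met | – | – | failure |
| Operator or device switched | – | met | – | failure |
| Study stopped by the anesthesiologist | – | – | met | failure |

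Only the first row depends on whether the threshold is two or three.

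**Size.** The documents give no attempt-level rates, so these inputs are assumptions:

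- n per arm: 219 (438/2, the group-sequential maximum) or 400 (800/2, a ceiling).
- p2, the proportion not intubated after two attempts: 0.01 to 0.03, equal in both arms.
- q, the proportion of third attempts that succeed: 1/2 to 2/3.
- s, the share of two-attempt failures given a third attempt by the same operator with the same device: 0.25 in one arm and 0.75 in the other, an illustrative extreme.
- d, the proportion failing by an earlier switch or stop: 0.01 to 0.03 in each arm, or 0 for the component alone.

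Patients failing two attempts, n × p2: 2.2 to 6.6 per arm at N=438, and 4 to 12 at N=800.

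Scored failures among them = n × p2 × (1 − s × q). The between-arm difference is n × p2 × q × (0.75 − 0.25):

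- N=438: 219 × 0.01 × 0.5 × 0.5 = 0.55, up to 219 × 0.03 × (2/3) × 0.5 = 2.19.
- N=800: 400 × 0.01 × 0.5 × 0.5 = 1.0, up to 400 × 0.03 × (2/3) × 0.5 = 4.0.
- If s is equal in both arms, the difference is 0 and the relative risk is 1.00.

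Relative risk for this component alone = (1 − 0.75q)/(1 − 0.25q):

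- q = 1/2: 0.625/0.875 = 0.71.
- q = 2/3: 0.500/0.833 = 0.60.

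Relative risk for the tested composite = [d + p2(1 − 0.75q)]/[d + p2(1 − 0.25q)]:

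- Lowest (d = 0.01, p2 = 0.03, q = 2/3): 0.025/0.035 = 0.71.
- Highest (d = 0.03, p2 = 0.01, q = 1/2): 0.03625/0.03875 = 0.94.

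Uncorrected chi-square on expected counts:

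- Smallest p (N=800, d = 0, p2 = 0.03, q = 2/3): 6.0 versus 10.0 failures of 400, p = 0.31.
- Largest p (N=438, d = 0.03, p2 = 0.01, q = 1/2): 7.94 versus 8.49 failures of 219, p = 0.89.

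**The case against.** The strongest reply is that the two numbers may not conflict. The two-attempt sentence comes after the one on failed initial attempts and the adjustments that follow. Read in that order, it could mean two more tries after a first failure, three in total, which would agree with the failure criterion and with a scale that counts to three and beyond. This reading stands as possible. It is not secure: the text does not say that the two are additional, and it speaks of initial attempts in the plural, so two more need not make three.

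A second reply is that an endpoint threshold need not equal a procedural limit, and that three attempts or a switch or stop is a coherent definition. That also stands, but the plan nowhere says the difference is intended.

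A reader might infer three stronger conclusions that the documents do not support:

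- **That the first criterion can never be met.** The procedure leaves later management to the anesthesiologist and permits, but does not require, a switch or stop. A third attempt is therefore not forbidden. The modified intent-to-treat set keeps every randomized patient in whom intubation was attempted, so a failed third attempt would count.
- **That a successful third attempt is certain to be scored a success.** It meets no criterion as written, but a centre that regards it as outside the study procedure could arguably record a discretionary stop.
- **That the mismatch biases the comparison or could produce a false positive.** Nothing in the documents suggests that third attempts would be used differently by arm, and even the extreme imbalance above stays far from 0.025.

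**Conclusion.** The inconsistency is real and minor. Two sections give different attempt limits, no text reconciles them, and one clinical course, a successful third attempt by the same operator with the same device, may be scored differently from a switch or stop after the same two failures.

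The reach is one secondary outcome and probably a few patients at most. The between-arm effect runs from zero upward: zero if third attempts are used equally and the arms are otherwise alike, and no more than about four patients at N=800 under the assumed extreme. These sizes rest wholly on the assumed p2, q, s and d. The primary outcome and sample size are unaffected, and third attempts remain visible in the attempts outcome. The case for acting is that failures are likely to be few, so a handful of reclassified patients can move the reported relative risk, and the correction is almost free.

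**What to change.** State one attempt limit in both the Protocol section and the failure definition, for all centres, before enrolment or, if enrolment has begun, before any unblinded look.

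- **If two is the limit:** define failure as not intubated within two attempts by the initial operator with the assigned device, or any earlier switch or stop. Two failed attempts are then a failure whatever follows. A switch or stop after the first attempt remains a matter of discretion.
- **If three is intended:** change the Protocol section to three attempts in total and leave the failure definition alone. A switch after two failures will still be scored differently from a successful third attempt, and the plan should accept that knowingly.

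Either way, keep counting all attempts in the attempts outcome. The cost is one line of protocol text and a case report form instruction, with no added patients or procedures.

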**Exploratory outcomes:**

- Portion of glottis opening score (POGO) score, defined as estimation of the glottis, which is visible during laryngoscopy (0, 25, 50, 75, 100%)
- Time to intubation, defined as the time between the laryngoscope introduced into oral cavity and cuff inflation (RSI definition) and to the first appearance of end-tidal CO2.
- Ease of intubation, defined as subjective evaluation of the anesthesiologist after finishing the intubation procedure: (1) very easy; (2) easy; (3) moderate; (4) difficult; and, (5) impossible.

**Safety outcomes:**

- Any apparent airway or dental injury including bleeding, airway trauma, dental fracture, aspiration, or bronchospasm.
- Incidence and severity of postoperative cough, assessed 2 hours after extubation in the PACU, and defined as continuous throat pain and rated as mild (less than a common cold), moderate (similar to a common cold), or severe (more than a common cold).

- Incidence and severity of postoperative sore throat, assessed after 2 hours of extubation in the PACU, defined as an acoustic quality that was different from the previous voice quality of the patients and rated as mild (less than a common cold), moderate (similar to a common cold), or severe (more than a common cold).
- Incidence and severity of postoperative hoarseness, assessed after 2 hours of extubation in the PACU, and rated as noticed by the patient only, apparent to an observer, or aphonia.

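### Postoperative cough is defined as throat pain and sore throat as a voice change, so two of the three symptom outcomes carry another symptom's definition and cough has none

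*Combined protocol and SAP*

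**What the plan says.** Objectives and Hypothesis lists the three postoperative symptoms as separate safety outcomes: "Incidence of postoperative coughing", "Incidence or severity of postoperative sore throat" and "Incidence or severity of postoperative hoarseness". It defines none of them.

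The Safety outcomes section is the only place that does:

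- **Cough:** "Incidence and severity of postoperative cough, assessed 2 hours after extubation in the PACU, and defined as continuous throat pain".
- **Sore throat:** "defined as an acoustic quality that was different from the previous voice quality of the patients".
- **Hoarseness:** no definition clause, only grades: "and rated as noticed by the patient only, apparent to an observer, or aphonia".

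Cough and sore throat share one severity scale, word for word: "rated as mild (less than a common cold), moderate (similar to a common cold), or severe (more than a common cold".

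The Protocol section says when patients are assessed after surgery but names no symptom. The Secondary outcomes part of the analysis plan says that exploratory and safety outcomes are reported by group without formal testing.

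**The concern.** Throat pain is not cough, and a changed voice is not a sore throat. The two clauses appear to sit one bullet too early: the throat-pain wording belongs with sore throat and the voice-quality wording with hoarseness. That leaves cough with no definition of its own.

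The safety comparison between the two devices is what could suffer. Applied literally, the cough row would show throat pain by arm, the sore-throat and hoarseness rows would both show voice change, and cough would go unmeasured.

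The Background, describing a systematic review, says videolaryngoscopy was associated with "fewer complications (e.g., laryngeal or airway trauma, postoperative hoarseness, hypoxia" among other benefits. Voice change is therefore a symptom on which the arms may differ. Such a difference would appear in two rows and could be read as two separate benefits, while a real difference in throat pain would be labelled cough.

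**Working it through.** The plan states no figure on this point, so there is none to reproduce. The check compares the definitions and then counts what they would record.

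**Step 1. The bullets side by side** (Safety outcomes section)

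| Outcome named | Definition attached | Symptom that definition describes |
|---|---|---|
| Cough | continuous throat pain | sore throat |
| Sore throat | altered voice quality | hoarseness |
| Hoarseness | grades only | hoarseness |

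Two of three carry another symptom's definition. Hoarseness remains usable, because its lowest grade (noticed only by the patient) serves as a threshold for presence.

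**Step 2. Does anything else settle the meaning?** The severity scale does not, because it is identical for cough and sore throat. The Objectives give names only, and the Protocol section names no symptom. Each misplaced clause lies inside one continuous sentence with its own symptom name, so a text-extraction fault is unlikely.

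**Step 3. What would be recorded.** Let c, p and v equal 1 if a patient has cough, throat pain and voice change respectively, and 0 otherwise.

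- As written: cough row = p; sore-throat row = v; hoarseness row = v.
- As intended: cough row = c; sore-throat row = p; hoarseness row = v.

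Rows are listed in the order cough, sore throat, hoarseness.

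| c, p, v | As written | As intended | Rows wrong |
|---|---|---|---|
| 0, 0, 0 | 0, 0, 0 | 0, 0, 0 | none |
| 1, 0, 0 | 0, 0, 0 | 1, 0, 0 | cough |
| 0, 1, 0 | 1, 0, 0 | 0, 1, 0 | cough, sore throat |
| 0, 0, 1 | 0, 1, 1 | 0, 0, 1 | sore throat |
| 1, 1, 0 | 1, 0, 0 | 1, 1, 0 | sore throat |
| 1, 0, 1 | 0, 1, 1 | 1, 0, 1 | cough, sore throat |
| 0, 1, 1 | 1, 1, 1 | 0, 1, 1 | cough |
| 1, 1, 1 | 1, 1, 1 | 1, 1, 1 | none |

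**Step 4. Counts**

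- The cough row is wrong when c ≠ p: 4 of 8.
- The sore-throat row is wrong when p ≠ v: 4 of 8.
- Both are wrong in 2 of 8, so at least one is wrong in 4 + 4 − 2 = 6 of 8.
- The hoarseness row is wrong in 0 of 8.
- All three rows are right only when c = p = v, which is 2 of 8.

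A patient with cough alone appears in no row. A patient with throat pain alone appears under cough. A patient with voice change alone appears under both sore throat and hoarseness.

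**The case against.** The harm needs an assessor to follow the definition clause over the plain name of the outcome. Most clinicians asked to score cough would score cough, and the displacement is easy to see. The symptom bullets also cite two published sources, which may hold the correct definitions; they are not available here. The six-of-eight count gives equal weight to combinations whose frequencies are unknown, and one of the two correct combinations is having no symptoms at all, so it could suggest more misrecording than would occur. The Background sentence on hoarseness comes from a review of patients with and without difficult airways, and the same section calls the benefit in rapid sequence intubation unclear. Finally, these outcomes are descriptive.

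Much of this stands, and it limits the point. The consequence is conditional on how assessors worked, the count says nothing about numbers of patients, and the Background supports only the possibility of a difference between arms.

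It does not remove the error. The operative definitions are wrong as written, and nothing in the documents corrects them. The trial has four centres in three countries. If some followed the written definition and others the ordinary meaning of the name, one row would mix different symptoms and a reader could not tell.

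**Conclusion.** The inconsistency is real and should be corrected. Two of the three postoperative symptom outcomes carry another symptom's definition, and cough is undefined. If the text is applied literally, six of the eight symptom combinations are misrecorded in at least one row; the number of patients cannot be estimated from the documents.

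The consequence rests on one assumption that cannot be checked here: that assessors, or a case report form repeating this wording, follow the definition clauses. The textual error itself does not depend on that assumption.

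No hypothesis test is affected, and neither are the primary result, the secondary analyses and the sample size. The airway and dental injury outcome in the same list is untouched. What is at stake is the trial's only planned report of these three symptoms by arm.

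**What to change.** - Move the throat-pain definition to sore throat.
- Move the voice-quality definition to hoarseness, keeping its existing grades.
- Write a separate definition for cough. At the same time, state whether cough is reported by incidence alone, as in the Objectives, or by incidence and severity, as in Safety outcomes.
- Make the same changes on any case report form that repeats the text.
- If any patient has already been assessed, find out which definitions each centre used, and report this before describing these outcomes by arm.

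The cost is wording in the protocol and on any case report form, with no added procedures, patients or visits. If assessments have begun, there is also a short check with the four centres.

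A separate minor clarification, not counted as an error: the Protocol section provides for up to two intubation attempts, while Secondary Outcomes scores failure against three. The two can be read together, but they should be reconciled, including whether the two attempts count the first. The number is for the investigators to state.
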